### **24-hour Coughs per Hour**

The 24-hour coughs per hour at Baseline and each post-Baseline visit are calculated as follows:

24-hour coughs per hour = Total number of cough events during the monitoring period (24-hour interval) / 24 hours (where the denominator may be different, as noted above, if the recording period is actually <24 hours but  $\geq 20$  hours)

As the change from baseline in 24-hour coughs per hour may have a skewed and wide distribution, the data will be (natural) log-transformed prior to analysis for the primary approach. The variable of change from baseline in log-transformed 24-hour coughs per hour will be used in the analysis of the primary endpoint. For each post-Baseline visit, the primary efficacy variable of analysis is defined as follows:

Change from baseline in log-transformed 24-hour coughs per hour  
= Log (24-hour coughs per hour at post-Baseline visit) – Log (24-hour coughs per hour at Baseline)

The primary analysis of the primary endpoint will be on the natural log scale of the cough rate data.

### **Awake Coughs per Hour**

Awake is time between waking up and sleep during the 24-hour monitoring period. The awake coughs per hour are defined as follows:

Awake coughs per hour = Total number of cough events during the monitoring period (24-hour interval) the participant is awake / Total duration (in hours) for the monitoring period the participant is awake

Similar to the primary efficacy variable, change from baseline in log-transformed awake coughs per hour will be used in the analysis and defined as below:

Change from baseline in log-transformed awake coughs per hour  
= Log (Awake coughs per hour at post-Baseline visit) – Log (Awake coughs per hour at Baseline)

### **Responders in 24-hour Coughs per Hour**

The responder variable in 24-hour coughs per hour is defined based on the magnitude of the percent change from baseline in the original scale at each post-Baseline visit:

Participant is considered a responder if the percent change from baseline in 24-hour coughs per hour is  $\leq -30\%$ ; participant is a non-responder otherwise.

The percent change from baseline in 24-hour coughs per hour is defined as follows:

Percent change in 24-hour coughs per hour  
= (Change from baseline in 24-hour coughs per hour/Baseline 24-hour coughs per hour)\*100%

### **Responders for ePRO Endpoints**

The responder variables in ePRO endpoints are defined based on the magnitude of the change from baseline at each post-Baseline visit:

- **LCQ total score**

Participant is considered a responder if change from baseline in LCQ total score is  $\geq 1.3$  point; non-responder otherwise

- **Mean weekly CSD total score**

1. Responder Endpoint 1: Participant is considered a responder if change from baseline in mean weekly CSD total score is  $\leq -1.3$ -point; non-responder otherwise
2. Responder Endpoint 2: Participant is considered a responder if change from baseline in mean weekly CSD total score is  $\leq -2.7$ -point; non-responder otherwise

- **Cough Severity VAS score**

Participant is considered a responder if change from baseline in Cough Severity VAS score is  $\leq -30$  mm; non-responder otherwise

## **9.5 Analysis Populations**

### **9.5.1 Efficacy Analysis Populations**

The FAS population will serve as the primary population for the analysis of efficacy data in this study. The FAS population consists of all randomized participants who have taken at least 1 dose of study intervention and provided at least 1 Baseline and at least 1 post-Baseline endpoint observation during the treatment period.

The PP population excludes participants due to important deviations from the protocol that may substantially affect the results of the primary efficacy endpoint. Potential deviations that may result in the exclusion of a participant from the PP population will be specified in the sSAP. The final determination on important protocol deviations, and thereby the composition of the PP population, will be made prior to the first unblinding of the database and will be documented in a separate memo. A supportive analysis using the PP population may be performed for the primary efficacy endpoint if the proportion of the participants with important protocol deviations is >10%.

Participants will be included in the treatment group to which they are randomized for the analysis of efficacy data using both the FAS and PP populations. Details on the approach to handling missing data are provided in Section 9.6.

### **9.5.2 Safety Analysis Population**

The APaT population will be used for the analysis of safety data in this study. The APaT population consists of all randomized participants who received at least 1 dose of study intervention. Participants will be included in the treatment group corresponding to the study intervention they actually received for the analysis of safety data using the APaT population. For most participants this will be the treatment group to which they are randomized. Participants who take incorrect study intervention for the entire treatment period will be included in the treatment group corresponding to the study intervention actually received.

At least 1 laboratory or vital sign measurement obtained subsequent to at least 1 dose of study intervention is required for inclusion in the analysis of each specific parameter. To assess change from baseline, a Baseline measurement is also required.

### **9.5.3 Pharmacokinetic Analysis Population**

The evaluable PK population for PK data analysis is defined as all participants with 1 measurable PK sample.

## **9.6 Statistical Methods**

This section describes the statistical methods that address the primary and secondary objectives. Methods related to exploratory objectives and supportive analyses will be described in the sSAP.

Statistical testing and inference for efficacy and safety analyses are described in Sections 9.6.1 and 9.6.2, respectively. Controlling of family-wise Type I error rate is described in Section 9.8. Unless otherwise stated, all statistical tests will be conducted at  $\alpha=0.0499$  (2-sided) level.

### 9.6.1 Statistical Methods for Efficacy Analyses

The analysis of efficacy endpoints will be based on the FAS population. Unless otherwise specified, all efficacy data, regardless of participant exposure to study intervention, will be included in efficacy analyses.

#### **Primary Efficacy Analysis**

Cough monitoring is conducted for baseline and 24 hours after administration of the study intervention on Weeks 4, 8, 12, 16, 20, and 24. The primary efficacy endpoint of this study is 24-hour coughs per hour at Week 24. As the change from baseline in 24-hour coughs per hour may have a skewed and wide distribution, the data will be log-transformed prior to analysis for the primary approach. The primary analysis of the primary endpoint will be on the natural log scale of the cough rate data. The variable of change from baseline in log-transformed 24-hour coughs per hour will be used in the analysis of the primary endpoint. A negative result indicates a decrease in cough rate, while a positive result indicates an increase in cough rate.

The primary analysis approach will be conducted utilizing the longitudinal ANCOVA model. In this model, the response vector consists of the change from baseline in log-transformed 24-hour coughs per hour at each post-Baseline visit. The model will include factors for treatment group, visit, the interaction of treatment group by visit, gender, and region; and the log-transformed baseline value and the interaction of log-transformed baseline value by visit as covariates. The model will use all available 24-hour coughs per hour data at baseline on Weeks 4, 8, 12, 16, 20, and 24. Contrasts will be constructed to compare each of the 2 MK-7264 treatment groups to the placebo group at each post-Baseline visit. The least squares mean change from baseline (in log scale) with the associated standard errors will be displayed for each treatment group. Estimated treatment differences (MK-7264 – placebo) along with corresponding 95% CIs will also be presented for each MK-7264 treatment group. In addition, the geometric mean of the 24-hour coughs per hour will be presented by treatment group and by visit. The percent difference in the change from baseline between MK-7264 and placebo will be estimated by  $100 * (e^{\text{diff}} - 1)$ , where diff is the difference provided by the analysis of the log transformed variable.

An observation of zero coughs per hour will be replaced by a cough rate of 0.1/hour for the calculation of geometric means. If this rule is used, the table will have a footnote detailing the participant(s) and treatment group(s) that had observations of zero coughs per hour.

Further details of the model specification, assumptions, and SAS implementation codes will be provided in the sSAP.

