#### 5.1 Inclusion Criteria

Participants are eligible to be included in the study only if all of the following criteria apply:

1. Chest radiograph or computed tomography scan of the thorax (within 5 years of Screening/Visit 1 and after the onset of chronic cough) not demonstrating any abnormality considered to be significantly contributing to the chronic cough or any other clinically significant lung disease in the opinion of the principal investigator or the sub-investigator (note: sub-investigator must be a physician).
2. Have chronic cough for  $\geq 1$  year and a diagnosis of refractory chronic cough or unexplained chronic cough as specified in Section 5.
3. Have a score of  $\geq 40$  mm on the Cough Severity VAS at both the Screening and Baseline visits, as specified in Section 8.2.2.

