#### **Data Handling Rules for Cough Data**

In general, each 24-hour session starts with awake status and is composed of an awake monitoring period and a sleep monitoring period. If a participant did not have a sleep time available before the end of the recording session, it will be considered that the participant was awake during the entire session. The last monitoring period of a session will be censored after the end time of the session.

The cough data will contain all cough events occurring during that 24-hour monitoring period as well as the information about “sleep time” and “awake time”. Any session with a

duration of recording <20 hours will be considered as missing. If a session has a duration less than 24 hours but no less than 20 hours, the 24-hour coughs per hour will be based on the actual duration of the session.

On each collection day, the cough counts, the actual cough monitoring duration (in hours), and the coughs per hour will be derived for the total 24-hour period, the awake period, and the sleep period, respectively.

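### Does limiting the 0.1/hour zero rule to geometric means leave zero-cough recordings without a value in the primary and awake cough models?

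*Combined protocol and SAP*

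**What the plan says.** Section 9.4.3 builds the primary variable from "Log (24-hour coughs per hour at post-Baseline visit" and the matching Baseline term, and the awake variable from "Log (Awake coughs per hour at post-Baseline visit" in the same way. Neither formula adds a constant. Section 9.6.1 uses the change in log rate as the response of the longitudinal ANCOVA and log Baseline as a covariate. The awake endpoint gets a similar model.

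The only rule for zeros is in Section 9.6.1, under Primary Efficacy Analysis: "An observation of zero coughs per hour will be replaced by a cough rate of 0.1/hour for the calculation of geometric means". It comes with a table footnote identifying the participants concerned. The cough data rules in Section 9.4.3 declare a session missing by its length alone: "duration of recording <20 hours will be considered as missing". A session of at least 20 hours with no cough is therefore valid data.

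Three other provisions bear on the point:

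- Section 9.6.1 says that efficacy data are used regardless of exposure and that the model takes all available cough data.
- It then leaves further model specification, assumptions and SAS code to the supplemental SAP.
- The responder rule divides "Change from baseline in 24-hour coughs per hour/Baseline 24-hour coughs per hour" and ends with the catch-all "participant is a non-responder otherwise".

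**The concern.** The log of zero is undefined, and most software would return a missing value. Read strictly, the zero rule serves a descriptive display that Section 9.6.1 presents in addition to the model estimates. A complete response could then enter the confirmatory model as missing data and be handled by the model-based approach in Table 4. The value given to the best possible outcome ought to be fixed before unblinding, because its effect on the test depends on which arm the zeros fall in.

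Two further points looked awkward:

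- **Zero baseline.** Entry requires at least 40 mm "on the Cough Severity VAS at both the Screening and Baseline visits" and cough for at least a year, but no minimum cough count. A participant with a zero Baseline recording could meet the Full Analysis Set condition of "at least 1 Baseline and at least 1 post-Baseline endpoint observation during the treatment period", yet have no log change at any of the six visits and a zero denominator in the percent change.
- **Ordering.** The constant 0.1/hour is higher than the rate from one or two coughs in 24 hours, so a silent recording would score as worse than a nearly silent one.

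**Working it through.** **Ordering.** The rate is coughs divided by recorded hours.

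- Over 24 hours: 1/24 = 0.042, 2/24 = 0.083 and 3/24 = 0.125 per hour. The constant corresponds to 0.1 × 24 = 2.4 coughs.
- Over the 20-hour minimum: 1/20 = 0.05 and 2/20 = 0.10, a tie.
- Over an assumed 16 waking hours: 1/16 = 0.063 and 2/16 = 0.125, so only a single cough falls below the constant.

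The reversal is real. As the rule is written, it reaches only the geometric means.

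**Inputs for size.** From Section 9.9: 430 per arm and 20% dropout, so 430 × 0.8 = 344 at Week 24; two-sided alpha 0.0499, so a critical z of 1.96; and power for the primary endpoint of 98% (15 mg) and above 99% (45 mg). The documents as released show no effect size, SD or frequency of zeros. The following are assumptions: baseline 20/hour (range 10 to 30), mean log change −1.0 on active and −0.5 on placebo, lognormal rates, and Poisson counts over 24 hours.

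**SD compatible with Table 6.** For a difference of 0.5 and 98% power:

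SD = 0.5 / [(1.961 + 2.054) × √(2/344)] = 0.5 / (4.015 × 0.07625) = 1.63.

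An SD of 2.0 would give z = 0.5/(2.0 × 0.07625) = 3.28 and power Φ(3.28 − 1.96) = 91%, which does not match Table 6.

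**Expected zeros in an active arm of 344.** The probability of a zero is E[exp(−24 × rate)], with log rate normal about ln(baseline) − 1.0.

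| SD | Baseline 20: probability | Baseline 20: expected zeros | Expected zeros, baseline 30 to 10 |
|---|---|---|---|
| 1.0 | 0.0006% | 0.002 | 0.0004 to 0.03 |
| 1.5 | 0.068% | 0.23 | 0.10 to 0.90 |
| 1.63 | 0.136% | 0.47 | 0.22 to 1.5 |
| 2.0 | 0.56% | 1.9 | 1.1 to 4.6 |

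**Effect of one zero kept at 0.1/hour.** The log change is ln(0.1/20) = −5.298. The shift in the arm mean is (−5.298 + 1.0)/344 = −0.0125, or 2.5% of the assumed difference of 0.5.

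**Keep versus drop.** Let f be the share of zeros in an arm and μ the mean log change among the rest.

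- Keep: m = (1 − f)μ + f × (−5.298); V = (1 − f)(SD² + μ²) + f × 5.298² − m²; z = difference in m / √[(V_active + V_placebo)/344].
- Drop: z = 0.5 / {SD × √[1/(344(1 − f_active)) + 1/(344(1 − f_placebo))]}.

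Worked case, SD 1.63 with one active zero (f = 1/344) and none on placebo: m_active = −1.0125, V_active = 2.703, V_placebo = 1.63² = 2.657. So z = 0.5125/√(5.360/344) = 4.11 if kept, against 4.02 if dropped.

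| SD | Active zeros | Placebo zeros | z keep | z drop |
|---|---|---|---|---|
| 1.63 | 1 of 344 | 0 | 4.11 | 4.02 |
| 1.63 | 1 of 344 | 1 of 344 | 3.97 | 4.02 |
| 2.0 | 0.6% | 0 | 3.43 | 3.27 |
| 2.0 | 0.6% | 0.3% | 3.32 | 3.27 |
| 2.0 | 0.6% | 0.6% | 3.22 | 3.27 |
| 1.0 | 1% | 0 | 6.83 | 6.54 |
| 1.0 | 1% | 1% | 5.94 | 6.52 |

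The last two rows are a stress test only. A zero share of 1% at SD 1.0 is about 1,500 times the modelled 0.0006%. The direction of the effect varies, and every z exceeds 1.96.

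**Limits of the check.** It is a two-sample comparison, not the full longitudinal model. It uses one SD both for the spread of rates and for the spread of change. It gives every zero a baseline of 20, whereas zeros would come mostly from participants with low baselines, where the shift per zero is smaller. Table 6 fixes the ratio of effect to SD at about 0.5/1.63 = 0.31 under this approximation. A smaller effect would therefore imply a smaller SD and fewer zeros, and a larger effect the reverse.

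**The case for a change.** The best case for acting is that Section 9.6 sets out the methods for the primary and secondary objectives, so the value assigned to a primary-endpoint observation belongs there. The sponsor foresaw zeros, since it wrote a rule for them, and one more clause would remove the doubt. Because the direction of the effect depends on which arm has the zeros, the choice should not remain open at unblinding. If the primary result fell close to the threshold, a shift in z of 0.05 to 0.1 could matter.

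Part of this stands: the protocol text alone does not define the model value, and it has to be settled before unblinding. But Section 9.6.1 assigns model specification and code to the supplemental SAP, and the coding of log(0) is that kind of detail. The reading is not evenly balanced either. The rule appears under the primary analysis, a geometric mean is the exponential of a mean log (the scale of the model), and the text asks for all available data.

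A broader remedy, setting every rate below 0.1/hour to 0.1, would restore the ordering only by overwriting genuine values of 0.042 and 0.083 per hour. A half-cough constant (0.5/24 = 0.021/hour) would keep the order, but it would place each zero ln(0.1/0.0208) = 1.57 log units further out. Each choice has a cost, and neither is clearly better than the sponsor's constant.

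**Conclusion.** No change follows. The zero rule is narrower in wording than the use analysts would naturally make of it, and the supplemental SAP is the place the plan names for such model detail. Whether that document settles the point cannot be checked here.

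Under the stated assumptions, and with a spread that agrees with Table 6, fewer than one zero is expected per active arm at a baseline of 20/hour, and about 1.5 at a baseline of 10/hour. One active-arm zero moves a z of about 4.0 by less than 0.1, in either direction. No scenario examined brings z near 1.96. This holds at the planned effect size and does not cover a borderline result.

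The zero-Baseline case needs someone with a year of chronic cough and a qualifying severity score to record no cough in 20 hours or more. If it occurred, the responder rule's catch-all already makes that participant a non-responder, and the same 0.1/hour value would give the model a finite log Baseline. The ordering point is arithmetically right but, as written, affects only descriptive geometric means, whose footnote would identify the zeros.

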### Secondary Efficacy Analysis

The continuous secondary efficacy endpoints will be analyzed using a similar longitudinal ANCOVA model as used for the primary efficacy analysis.

As the change in awake coughs per hour may have a skewed and wide distribution, the data will be log-transformed (natural log) prior to analysis. The variable of change from baseline in log-transformed awake coughs per hour will be used in the analysis.

Responder endpoints will be analyzed by the logistic regression model. The model will include terms for treatment group, visit, the interaction of treatment group by visit, gender, region, baseline, and the interaction of baseline by visit for the underlying continuous response. Log odds ratio will be back transformed into odds ratio for final reporting.

Table 4 summarizes the analysis strategy of the primary and key secondary efficacy endpoints.

Table 4 Analysis Strategy for Primary and Key Secondary Efficacy Endpoints

Endpoint/Variable (At Week 24)	Statistical Method	Missing Data Approach
Primary		
24-hour coughs per hour	Longitudinal ANCOVA	Model-based a
Secondary		
Awake coughs per hour	Longitudinal ANCOVA	Model-based a
Proportion of participants with a $\geq 1.3$ point increase from baseline in LCQ total score	Logistic Regression	Model-based a
Proportion of participants with a $\geq 30\%$ reduction from baseline in 24-hour coughs per hour	Logistic Regression	Model-based a
Proportion of participants with a $\geq 1.3$ point reduction from baseline in mean weekly CSD total score	Logistic Regression	Model-based a
Proportion of participants with a $\geq 2.7$ point reduction from baseline in mean weekly CSD total score	Logistic Regression	Model-based a
Proportion of participants with a $\geq 30$ mm reduction from baseline in Cough Severity VAS score	Logistic Regression	Model-based a
a Includes data collected after intervention discontinuation. ANCOVA = analysis of covariance; CSD = Cough Severity Diary; LCQ = Leicester Cough Questionnaire; VAS = Visual Analogue Scales.		

The strategy to address multiplicity issues with regard to multiple treatment comparisons, multiple efficacy endpoints, multiple timepoints, and interim analyses is described in Sections 9.7 and 9.8.

## **Handling of Missing Data**

The missing data approach is specified in the above mentioned primary and secondary efficacy endpoints analysis sections. All other analyses will be conducted based on the observed data only. Additional sensitivity analyses with respect to the handling of missing data will be specified in the sSAP.

### **9.6.2 Statistical Methods for Safety Analyses**

The safety endpoints will be analyzed based on the data collected in the Main study period, as well as based on the cumulative data collected across both the Main and Extension study periods.

Safety and tolerability will be assessed by clinical review of all relevant parameters including AEs, laboratory tests, and vital signs.

The analysis of safety results will follow a tiered approach (Table 5). The tiers differ with respect to the analyses that will be performed. Tier 1 safety endpoints will be subject to inferential testing for statistical significance with p-values and 95% CIs provided for between-group comparisons. Tier 2 safety endpoints will be evaluated via point estimates and 95% CIs for between-group comparisons. Tier 3 safety endpoints will be evaluated via point estimates only.

Taste-related AEs (including dysgeusia, ageusia, and hypogeusia, as well as other related terms) will be classified as belonging to “Tier 1”. The unadjusted p-values and point estimates with 95% CIs from the pairwise comparison between each of MK-7264 dose versus placebo will be provided. The definition of taste-related AEs will be finalized and documented before the database lock of the Main study period.

The frequency of taste-related AEs across pre-defined time intervals will be provided, where the time intervals will be defined as: >0 to ≤1 week, >1 to ≤4 weeks, >4 to ≤8 weeks, >8 to ≤12 weeks, >12 to 16 weeks, >16 to 20 weeks, and >20 to 24 weeks in the Main study period; and >24 to ≤38 weeks, and >38 to ≤52 weeks in Extension study period. In each time interval, the denominator for calculation of percentage will be the number of participants exposed at the beginning of the time interval and the numerator will be the number of participants with at least 1 taste related AE occurring in this time interval. Only the first event will be counted and all recurrent events will not be included.

The broad clinical and laboratory AE categories consisting of the percentage of participants with any AE, a drug related AE, a serious AE, an AE which is both drug-related and serious, an oral paresthesia AE, an oral hypoesthesia AE, and who discontinued due to an AE will be classified as belonging to “Tier 2”.

Adverse experiences (specific terms as well as system organ class terms) and predefined limits of change in laboratory, and vital signs will be classified as belonging to “Tier 2” or “Tier 3”, based on the number of events observed. Membership in Tier 2 requires that at least

4 participants in any treatment group exhibit the event; all other adverse experiences and predefined limits of change will belong to Tier 3.

The threshold of at least 4 events was chosen because the 95% CI for the between-group difference in percent incidence will always include zero when treatment groups of equal size each have less than 4 events and thus would add little to the interpretation of potentially meaningful differences. Because many 95% CIs may be provided without adjustment for multiplicity, the CIs should be regarded as a helpful descriptive measure to be used in review, not a formal method for assessing the statistical significance of the between-group differences in adverse experiences and predefined limits of change.

The Tier 1 and Tier 2 safety endpoints will be analyzed using the Miettinen & Nurminen method [Miettinen, O. and Nurminen, M. 1985].

Continuous measures such as changes from baseline in laboratory and vital signs will be considered Tier 3 safety parameters.

Summary statistics for baseline, on treatment, and change from baseline values will be provided by treatment group in table format.

Table 5 Analysis Strategy for Safety Parameters

Safety Tier	Safety Endpoint a	p-value	95% CI for Treatment Comparison	Descriptive Statistics
Tier 1	Any taste-related AE	X	X	X
Tier 2	Any oral paresthesia AE		X	X
	Any oral hypoesthesia AE		X	X
	Any AE		X	X
	Any Serious AE		X	X
	Any Drug-related AE		X	X
	Any Serious and Drug-related AE		X	X
	Discontinuation due to AE		X	X
Tier 3	Specific AEs, SOCs, or PDLCs b (incidence ≥4 participants in 1 of the treatment groups)		X	X
	Specific AEs, SOCs, or PDLCs b (incidence <4 participants in all the treatment groups)			X
	Change from baseline results (Labs, Vital Signs)			X

[figure not shown]
a Adverse experience references refer to both clinical and laboratory AEs.  
 b Includes only those endpoints not pre-specified as Tier 1 or not already pre-specified as Tier 2 endpoints.  
 AE = adverse event; CI = confidence interval; PDLC = Pre-defined Limit of Change; SOC = System Organ Class;  
 X = results will be provided.

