## 9.8 Multiplicity

### Primary and Key Secondary Endpoints

Due to the interim analysis for futility, an  $\alpha$ -spending of 0.0001 will be applied to the 2-sided Type I error rate of 0.05 for the primary and secondary hypotheses based on the Haybittle Peto method [Haybittle, J. L. 1971] [Peto, R., et al 1976]. Multiplicity adjustment will be made for testing 2 doses on the primary and the key secondary endpoints for the analysis, ie, for testing a family of the following hypotheses:

- H11: MK-7264 45 mg BID is superior to placebo in reducing 24hour coughs per hour at Week 24
- H12: MK-7264 15 mg BID is superior to placebo in reducing 24-hour coughs per hour at Week 24
- H21: MK-7264 45 mg BID is superior to placebo in reducing awake coughs per hour at Week 24
- H22: MK-7264 15 mg BID is superior to placebo in reducing awake coughs per hour at Week 24
- H31: MK-7264 45 mg BID is superior to placebo on the proportion of participants with a  $\geq 1.3$ -point increase from baseline in LCQ total score at Week 24
- H32: MK-7264 15 mg BID is superior to placebo on the proportion of participants with a  $\geq 1.3$ -point increase from baseline in LCQ total score at Week 24
- H41: MK-7264 45 mg BID is superior to placebo with respect to the proportion of participants with a  $\geq 30\%$  reduction from baseline in 24-hour coughs per hour at Week 24
- H42: MK-7264 15 mg BID is superior to placebo with respect to the proportion of participants with a  $\geq 30\%$  reduction from baseline in 24-hour coughs per hour at Week 24

To strongly control the Type I error rate for this family, a step down testing procedure will be applied in the order specified above. Each hypothesis will be formally tested only if the preceding one is significant at  $\alpha=0.0499$  level.

[figure not shown]
[Redacted], [Table 6](#) provides power for the primary and key secondary efficacy endpoints with a total of 1290 participants (430 participants per treatment group). All calculations are based on 2-sided  $\alpha=0.0499$  significance level. The dropout rate is expected to be 20% at Week 24.

Table 6 Power for the Primary and Key Secondary Efficacy Endpoints

Endpoints (At Week 24)	Power in MK-7264 45 mg BID Group	Power in MK-7264 15 mg BID Group
24-hour coughs per hour	>99%	98%
Awake coughs per hour	98%	97%
Proportion of participants with $\geq 1.3$ -point increase from baseline in LCQ total score	81%	56%

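### Section 9.6.2 reports taste-related AEs over time as plain percentages in intervals of 1, 3, 4 and 14 weeks, so cells of different width, and Main versus Extension in particular, cannot be compared

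*Combined protocol and SAP*

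**What the plan says.** Section 9.6.2 (Statistical Methods for Safety Analyses) makes taste-related AEs the Tier 1 safety event. Besides the comparison of each dose with placebo, it plans their frequency in nine consecutive intervals. The first four are ">0 to ≤1 week, >1 to ≤4 weeks, >4 to ≤8 weeks, >8 to ≤12 weeks". The next three are ">12 to 16 weeks, >16 to 20 weeks, and >20 to 24 weeks in the Main study period". The last two are ">24 to ≤38 weeks, and >38 to ≤52 weeks in Extension study period".

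The cell content is defined in three statements:

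- Denominator: "the denominator for calculation of percentage will be the number of participants exposed at the beginning of the time interval".
- Numerator: "the numerator will be the number of participants with at least 1 taste related AE occurring in this time interval".
- Event rule: "Only the first event will be counted and all recurrent events will not be included".

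The section gives no rate per person-time, no adjustment for interval width and no time-to-onset analysis. Section 9.12 summarises days on therapy descriptively but does not link them to AE incidence. Section 9.6 leaves supportive analyses to the supplemental SAP, which is not among the documents.

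**The concern.** A table by time interval is made to be read across, to see when an event starts and whether it fades. Here observation time per cell varies 14-fold, and the largest absolute change in width, from 4 to 14 weeks, falls exactly where the Main period ends and the Extension begins. A wider cell collects more onsets at the same underlying rate, so the percentages move with time even when the risk does not.

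This matters because safety and tolerability is a primary objective (Section 3), taste-related AEs were the most frequent AEs in earlier studies (Section 2.3), dysgeusia is described as dose related (Section 4.3.1), and the Extension is there to assess longer-term safety and tolerability (Section 4.3.3). Read without regard to width, the table could support a statement that taste disturbance keeps emerging, or increases, after Week 24 when onset is steady or falling.

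**Working it through.** The plan gives no numerical result for this table, so there is no figure to reproduce. The check is what the table would show under a known onset rate.

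**Inputs from the documents.** The interval limits give widths of 1, 3, 4, 4, 4, 4, 4, 14 and 14 weeks. They add up correctly: 1 + 3 + 5 × 4 = 24 weeks (Main) and 14 + 14 = 28 weeks (Extension). For dropout, the power paragraph before Table 6 says "The dropout rate is expected to be 20% at Week 24". If exponential, that is d = −ln(0.80)/24 = 0.0093 per week.

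**Assumptions.** The documents state no onset rate, so the 4-week onset risk r is varied from 0.5% to 20%. The weekly hazard is constant, L = −ln(1 − r)/4. An AE is counted in the interval in which it starts. In the dropout case, exposure is lost at rate d, also in the Extension.

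**Step at Week 24** (percentage in >24 to 38 weeks divided by percentage in >20 to 24 weeks):

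- A, only participants still at risk in the denominator, no dropout: (1 − e^(−14L)) / (1 − e^(−4L)).
- B, all exposed participants in the denominator, first event overall in the numerator, no dropout: A × e^(−4L).
- D, as B, with dropout at rate d within the interval: e^(−4L) × (1 − e^(−14(L+d))) / (1 − e^(−4(L+d))).

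| Onset risk per 4 weeks | A | B | D |
|---|---|---|---|
| 0.5% | 3.48 | 3.46 | 3.31 |
| 1% | 3.46 | 3.42 | 3.27 |
| 2% | 3.41 | 3.35 | 3.20 |
| 5% | 3.29 | 3.12 | 2.99 |
| 10% | 3.08 | 2.78 | 2.66 |
| 20% | 2.71 | 2.17 | 2.09 |

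The upper limit is the width ratio, 14/4 = 3.5. The range over these assumptions is therefore about 2.1 to 3.5.

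**Example at 2% per 4 weeks, method A.** L = −ln(0.98)/4 = 0.00505 per week. The nine cells read 0.5, 1.5, 2.0 (five times), 6.83 and 6.83%. The step from the 1-week to the 3-week cell is also about 3-fold (2.98) from width alone.

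**What a real fall would look like.** Under A the two cells are equal when the Extension rate is 4/14 = 0.286 of the Main rate, a fall of 71.4%. A halved rate appears as a rise of (1 − e^(−7L))/r: 1.74-fold at 2%, and 1.62 to 1.75-fold over the whole range. A fall of 80% appears as a drop (ratio 0.70 to 0.72). Solving the same equality under D, the break-even fall is 69.5% at 2% and 61% at 20%, so 71% is the upper end.

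**Between the two Extension cells.** These have equal width, so a halving shows: (1 − e^(−7L)) / (1 − e^(−14L)) = 0.51 at 2% and 0.55 at 10%.

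**The case against.** The strongest reply is that little hangs on this table. It is descriptive, its limits are fixed in advance, and no test is attached to it. The Tier 1 comparison of any taste-related AE with placebo does not use it. All arms share the intervals, so dose against placebo within a cell has the same nominal width. The 14-week limits coincide with the Extension site visits at Weeks 38 and 52, which is a recognisable reason for choosing them. All of this stands, and it limits the point to a cheap improvement. It does not make cells of 4 and 14 weeks comparable within an arm, which is how a table over time is read.

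Four stronger readings are tempting, and the documents do not support them:

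- A reader might expect a jump of one particular size, such as 3.4-fold. That needs an onset risk of about 2% per 4 weeks, an at-risk denominator and no dropout; the plan states neither of the first two and expects 20% dropout.
- A reader might infer that any decline in the Extension is hidden. Only a Main-to-Extension fall below the break-even is. Among the five 4-week cells, and between the two 14-week cells, width does not distort the trend.
- A reader might add the change in contact frequency, from every 4 to every 7 weeks, as further inflation. Participant comment cards capture AEs between visits (Section 8.1.6), and fewer contacts would if anything lower the Extension figures.
- A reader might say the plan has no other description of onset. None is in these documents, but the supplemental SAP may hold one.

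**Conclusion.** The concern holds in limited form. Cells of different width in this table cannot be compared over time. At a constant onset rate the Week 24 step would be about 2 to 3.5-fold from width alone. The direction follows from the stated intervals; the size rests on an assumed onset risk of 0.5% to 20% per 4 weeks, a constant hazard, the reading of the denominator, and the use of the stated dropout for loss of exposure. A fall in onset rate from Main to Extension smaller than about 71% (somewhat less at high onset rates with all exposed participants in the denominator) would be hidden or shown as a rise.

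A related ambiguity should be settled at the same time: the text does not say whether the first event is first overall or first within the interval. If first overall, earlier cases who are still exposed stay in the denominator and pull later percentages down. At 2% per 4 weeks and a constant rate, the five 4-week cells would then drift from 1.96 to 1.81%.

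No efficacy analysis and no test against placebo is affected.

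**What to change.** In Section 9.6.2:

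1. State that the first event means the participant's first taste-related AE overall.
2. For each interval and arm, add the number of first onsets divided by person-weeks on drug and still free of a prior taste-related AE, expressed per 100 participants per 4 weeks.
3. Keep the planned percentage as a secondary column.
4. Base any statement on onset over time, or on Main versus Extension, on the rate.

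A constant onset rate then gives the same value in every cell: at 2% per 4 weeks, 0.505 per 100 person-weeks, or 4 × 0.505 = 2.02 per 100 participants per 4 weeks. A halved Extension rate shows as a ratio of 0.5.

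The at-risk condition is essential. Dividing first-overall onsets by all person-weeks on drug would produce a false decline. With no dropout, Weeks 38 to 52 relative to Week 1 would be e^(−38L) × (1 − e^(−14L)) / 14 ÷ (1 − e^(−L)), which is 0.80 at 2%, 0.57 at 5% and 0.31 at 10%. These are apparent falls of 20%, 43% and 69% with no change in risk.

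The cost is a few sentences, one extra column and slightly more programming, using AE onset and dosing dates already collected.
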